- Sampling schedule for **neonates/infants:** Surveillance for RSV LRTI will be conducted in infants through the 12 month study period. During this 1-year post-birth surveillance period, for each RTI with suspicion of difficulty in breathing, or wheezing, or with parental concern, a nasal swab will be collected at a visit to assess potential RSV associated RTIs/LRTIs.
- Primary Completion Date (PCD): 42 days post-delivery/birth (i.e. Visit 6 for maternal subjects and Visit 2-NB for infant subjects) or last visit of Epoch 002.
- End of Study (EoS): Last testing results released of samples collected up to Visit 4-NB (assays related to primary and secondary endpoints).
- Duration of the study: Approximately 4.5 to 6 months for maternal subjects; approximately 1 year for infant subjects.
 - Epoch 001: Screening
 - Epoch 002: Primary starting at Visit 1 and ending 42 days post-delivery/birth (Visit 6 for maternal subjects and Visit 2-NB for infant subjects).*
 - Epoch 003: Follow-up of infants starting 43 days post-delivery/birth and ending at Visit 4-NB (1 year post-birth).

*Any safety and disease surveillance data collected after Visit 2-NB will be collected in Epoch 003.

Table 2 Study groups and epochs foreseen in the study

Study Groups	Number of subjects enrolled	Age (Min/Max)	Epochs		
			Epoch 001	Epoch 002	Epoch 003
Maternal subjects	Up to ~ 2300	18 years - 45 years	x	x	
Infants	Up to ~ 2300	NA		x	x

Approximately 200 to 300 per country. To achieve the enrollment targets noted above, the number of pregnant women SCREENED in each country may exceed the country-specific enrolment goal.

- Surveillance for pregnancy outcomes and pregnancy-related events of interest that occur from Visit 1 up to 42 days after delivery (Visit 6).
- Surveillance for neonatal events of interest that occur from birth up to 28 days of age.
- Surveillance for RSV LRTI and RSV hospitalization in infants, from birth up to 1 year of age. Nasal swabs will be collected during surveillance visits to confirm RSV positivity.

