- This study includes active and passive surveillance of RSV LRTI. In an active surveillance, site personnel will contact the subject's parent(s) / LAR(s) or their designate(s). Active contacts will occur at regular intervals (depending on RSV seasonality at the site) and will be scripted. In a Passive contact, the subject's parent(s) / LAR(s) or their designate(s) contact site personnel if their infant has any of the RTI symptoms (cough, runny nose, or blocked nose). Site personnel will use a script to guide data collection once a passive contact has been made. In each case, the site will use the decision tree (Figure 2 of protocol) to determine if a case assessment visit is needed (Occurrence of Surveillance contact flag and Surveillance Contact Report form in the eCRF). If the patient reported wheezing or difficulty breathing, the nurse will set up an appointment for the mother to bring her infant for follow up at the clinic within three days of the beginning of symptoms. Once the child has completed an assessment visit, site personnel will continue surveillance for the case episode. If the child's symptoms have deteriorated and the child is admitted to the hospital or needs oxygen therapy (Inpatient and Worsening flag in the eCRF), the physician will report worsening symptoms (Worsening form in the eCRF). Start dates will be recorded for cough, runny nose, wheezing, and difficulty breathing, but only end dates will be recorded for cough and difficulty breathing. If the infant experiences new bouts of cough or blocked nose after 7 days of her/his recovery from the last RTI symptoms, then a new case assessment form will be opened. Given that infants frequently experience runny nose, a case can be concluded even if the runny nose has not resolved.

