2.2. Case Definitions

The case definitions are summarized in the following table: (see section [9.4](#) for detailed derivation of case definition).

Table 3 RTI/LRTI case definitions

RSV-RTI	(Runny nose, OR Blocked nose, OR Cough) AND Confirmed RSV infection ⁴
RSV-LRTI	(History of cough OR difficulty in breathing ¹) AND (SpO ₂ < 95% ² , OR RR increase ³) AND Confirmed RSV infection ⁴
RSV-severe LRTI	Meeting the case definition of RSV-LRTI AND SpO ₂ < 93%, OR lower chest wall in-drawing
RSV-very severe LRTI	Meeting the case definition of RSV-LRTI AND (SpO ₂ < 90%, OR inability to feed OR failure to respond / unconscious)
RSV hospitalization	Confirmed RSV infection ⁵ AND Hospitalized for acute medical condition ⁶
All-cause RTI	Runny nose, OR Blocked nose, OR Cough
All-cause LRTI	(History of cough OR difficulty in breathing ¹) AND (SpO ₂ < 95% ² , OR RR increase ³)

RTI = respiratory tract illness; LRTI = lower respiratory tract illness; RR = respiratory rate; SpO₂ = blood oxygen saturation by pulse oximetry.

¹ Based on history reported by parents/LARs and includes difficulty in breathing (e.g. showing signs of wheezing or stridor, tachypnoea, flaring [of nostrils], chest in-drawing, apnoea).

² For blood oxygen saturation (SpO₂), the lowest value monitored will be used. In high altitudes (>2500m), SpO₂ <92% for LRTI, <90% for severe LRTI, <87% for very severe LRTI.

³ RR increase defined as:

- > 60/minute (< 2 months of age)
- > 50/minute (2 to < 12 months of age)
- > 40/minute (12 to 24 months of age)

⁴ RSV infection confirmed on nasal swab positive for RSV A or B by quantitative reverse transcription polymerase chain reaction (qRT-PCR).

⁵ RSV sampling and testing from nasal swabs.

⁶ Hospitalization is defined as admission for observation or treatment based on the judgement of a health care provider

Table 4 RTI/LRTI case definitions including site altitude

	Altitude	
	≤2500m	>2500m
RSV-RTI	Runny nose, OR Blocked nose, OR Cough AND Confirmed RSV infection ⁴	Runny nose, OR Blocked nose, OR Cough AND Confirmed RSV infection ⁴
RSV-LRTI	History of cough OR difficulty in breathing ¹ AND SpO ₂ < 95% ² , OR RR increase ³ AND Confirmed RSV infection ⁴	History of cough OR difficulty in breathing ¹ AND SpO ₂ < 92% ² , OR RR increase ³ AND Confirmed RSV infection ⁴
RSV-severe LRTI	Meeting the case definition of RSV-LRTI AND SpO ₂ < 93%, OR lower chest wall in-drawing	Meeting the case definition of RSV-LRTI AND SpO ₂ < 90%, OR lower chest wall in-drawing

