9.4.2. RSV LRTI

The child will be reported positive for RSV LRTI when he/she presents with at least one of the following symptoms: (The data can be pulled from the Case Assessment Visit)

- Cough reported during the case assessment visit. Variables will be pulled from [frmSURVEILLANCE_CONTACT] (field [ASSESS_VIS]= 'YES') and [frmSYMPTOMS_RTI] (fields [ASSESS_VIS]= 'Yes' and [sctSYMPTOMS_RTI]= 'COUGH')
- Difficulty breathing reported during the case assessment visit. Variables will be pulled from [frmSURVEILLANCE_CONTACT] (field [ASSESS_VIS]= 'YES') and [frmSYMPTOMS_RTI] (fields [ASSESS_VIS]= 'Yes' and [sctSYMPTOMS_RTI]= 'BREATHING')

AND at least one of following symptoms: **(The data can be pulled from the Case Assessment Visit OR Worsening Visits. If worsening visits took place for this episode, the most severe value of SpO₂ or RR will be used, whether it was observed in the Case Assessment Visit or the Worsening Visit.)**

- SpO₂(<95% if altitude ≤2500m and <92% if altitude >2500m) during the physical examination of case assessment visit. (field [scOXYGEN_SATURATION_RTI] OR [scOXYGEN_SATURATION_WOR]=[SpO₂] < '95.0% or <92%')

OR

- RR increase (field [sctRESPIRATORYRATE_RTI]=[VSORRES_RESP] OR [sctRESPIRATORYRATE_WOR]=[VSORRES_RESP_WOR])

RR increase defined as:

- > 60/minute (< 2 months of age)
- > 50/minute (2 to < 12 months of age)
- > 40/minute (12 to 24 months of age)

AND

Confirmed RSV infection from a nasal swab test.

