9.4.2.1. Start date of RSV-LRTI

Start dates of RSV LRTI symptoms will be pulled from the Case Assessment Visit for at least one of the following: parental report of history of cough or difficult breathing. The start date of RSV LRTI is the earliest of the start dates of the following symptoms:

- Cough

Variables will be pulled from [frmSURVEILLANCE_CONTACT] (field [ASSESS_VIS]= 'YES') and [frmSYMPTOMS_RTI] (fields [ASSESS_VIS]= 'Yes' and [sctSYMPTOMS_RTI]= 'COUGH' and [cmpCOUGH_DT]= 'SRDAT')

Or

- Difficulty Breathing

Variables will be pulled from [frmSURVEILLANCE_CONTACT] (field [ASSESS_VIS]= 'YES') and [frmSYMPTOMS_RTI] (fields [ASSESS_VIS]= 'Yes' and [sctSYMPTOMS_RTI]= 'BREATHING' and [cmpBREATHING_DT]= 'SRDAT')

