9.4.7. All cause LRTI

All cause LRTI is reported if the child has one or more of the following:

- COUGH reported during the case assessment visit. Variables will be pulled from [frmSURVEILLANCE_CONTACT] (field [ASSESS_VIS]= 'YES') and [frmSYMPTOMS_RTI] (fields [ASSESS_VIS]= 'Yes' and [sctSYMPTOMS_RTI]= 'COUGH')
- Difficulty breathing reported during the case assessment visit. Variables will be pulled from [frmSURVEILLANCE_CONTACT] (field [ASSESS_VIS]= 'YES') and [frmSYMPTOMS_RTI] (fields [ASSESS_VIS]= 'Yes' and [sctSYMPTOMS_RTI]= 'BREATHING')

AND

(The data for below can be pulled from the Case Assessment Visit OR Worsening Visits. If worsening visits took place for this episode, the most severe value of SpO₂ or RR will be used, whether it was observed in the Case Assessment Visit or the Worsening Visit.)

- SpO₂(<95% if altitude ≤2500m and <92% if altitude >2500m) during the physical examination of case assessment visit. (field [scOXYGEN_SATURATION_RTI] OR [scOXYGEN_SATURATION_WOR]=[SpO₂]< '95.0%' or <92%)
OR
- RR increase (field [sctRESPIRATORYRATE_RTI]=[VSORRES_RESP] OR [sctRESPIRATORYRATE_WOR]=[VSORRES_RESP_WOR])

RR increase defined as:

- > 60/minute (< 2 months of age)
- > 50/minute (2 to < 12 months of age)
- > 40/minute (12 to 24 months of age)

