9.4.8. Alternative LRTI

The child will be reported positive for Alternative LRTI when he/she presents with at least one of the following symptoms: (The data can be pulled from the Case Assessment Visit under signs and symptoms).

- Crackles reported during the case assessment visit. Variables will be pulled from [frmSIGNSANDSYMPTOMS] [sctAUSCULTATION_RTI] [CRACKLES_AUSC]= “Y”)
- OR
- wheeze reported during the case assessment visit. Variables will be pulled from [frmSURVEILLANCE_CONTACT] (field [ASSESS_VIS]= ‘YES’) and [frmSYMPTOMS_RTI] (fields [ASSESS_VIS]= ‘Yes’ and [sctSYMPTOMS_RTI]= ‘wheezing’)

AND at least one of following symptoms: **(The data can be pulled from the Case Assessment Visit OR Worsening Visits. If worsening visits took place for this episode, the most severe value of SpO₂ or RR will be used, whether it was observed in the Case Assessment Visit or the Worsening Visit.)**

- SpO₂(<95% if altitude ≤1800m and <92% if altitude >1800m) during the physical examination of case assessment visit. (field [scOXYGEN_SATURATION_RTI] OR [scOXYGEN_SATURATION_WOR]=[SpO₂]< ‘95.0% or <92%’)

OR

- RR increase (field [sctRESPIRATORYRATE_RTI]=[VSORRES_RESP] OR [sctRESPIRATORYRATE_WOR]=[VSORRES_RESP_WOR])

RR increase defined as:

- > 60/minute (< 2 months of age)
- > 50/minute (2 to 6 months of age)

OR

New onset apnea Variable pulled from

[frmSIGNSANDSYMPTOMS] [sctSeverity_SIGNS_RTI]

OR

Nasal flaring

[frmSIGNSANDSYMPTOMS_WOR] [sctRESPIRATORY_SIGNS_RTI]

OR Intercostal recession (in place of retractions)

[frmSIGNSANDSYMPTOMS_WOR] [sctRESPIRATORY_SIGNS_RTI]

OR Grunting

[frmSIGNSANDSYMPTOMS_WOR] [sctRESPIRATORY_SIGNS_RTI]

AND

Confirmed RSV infection from a nasal swab test.

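### The LRTI definition counts parent-reported wheeze as difficulty in breathing, but sections 9.4.2 and 9.4.7 never read the separately recorded wheezing item, so an infant reported only with wheeze can be a case by Table 3 and a non-case in the analysis

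*SAP*

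**What the plan says.** All references are to the current SAP (Amendment 2) unless stated.

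- **Definition.** In section 2.2, Tables 3 and 4 admit an infant to RSV-LRTI or all-cause LRTI on cough or difficulty in breathing, plus low SpO2 or raised respiratory rate, plus confirmed RSV for RSV-LRTI. Footnote 1 bases the first limb on parental history and says that it "includes difficulty in breathing (e.g. showing signs of wheezing or stridor, tachypnoea, flaring [of nostrils], chest in-drawing, apnoea".
- **Derivation.** Section 9.4.2 takes the first limb from two entries in the symptom section of the case assessment: `COUGH`, and `BREATHING`, described as "Difficulty breathing reported during the case assessment visit". Section 9.4.7, which opens "All cause LRTI is reported if the child has one or more of the following", lists the same two entries.
- **Dates.** Section 9.4.2.1 takes the start date from "parental report of history of cough or difficult breathing", and 9.4.7.1 uses the same two symptoms. The general text of 9.4 says that the earliest reported symptom date starts the episode.
- **Data collected.** Section 2.1 says: "Start dates will be recorded for cough, runny nose, wheezing, and difficulty breathing". It records end dates only for cough and difficulty breathing. Its sampling schedule also treats wheezing as an alternative to difficulty in breathing: "for each RTI with suspicion of difficulty in breathing, or wheezing, or with parental concern, a nasal swab will be collected".
- **Severity levels.** Sections 9.4.3 and 9.4.4 require the RSV-LRTI definition to be met first.

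**The concern.** The definition uses difficulty in breathing as an umbrella term that includes wheeze. The derivation uses one item with that name and ignores the wheezing item beside it. If a site records wheeze in its own item and leaves `BREATHING` blank, the programmed endpoint is narrower than the one the SAP says it applies.

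The secondary incidence endpoints are at stake: all, severe and very severe RSV-LRTI. So is the all-cause LRTI rate that section 5.3.6.2 adds. The start-date rule has the same gap, and there it can also touch episodes that are counted. An infant whose wheeze came before the cough has an earlier date on record that the LRTI start date does not use, contrary to the general rule in 9.4.

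**Working it through.** The SAP gives no figure on this point, so there is none to reproduce. The check compares the definition with the derivation pattern by pattern, holding the SpO2 or respiratory-rate limb and RSV confirmation as met.

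**Step 1. Is wheezing a separate item?** Section 2.1 gives it its own start date. The swab trigger lists it as an alternative ("for each RTI with suspicion of difficulty in breathing, or wheezing, or with parental concern"). Sections 5.3.7.2 and 5.4.1.2 give it its own row in the symptom tables. The superseded Amendment 1, used here only as evidence of how the form is built, reads "wheeze reported during the case assessment visit" from the same symptom section that holds `COUGH` and `BREATHING`. So the data exist.

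**Step 2. Three reported items: cough, `BREATHING`, wheeze.**

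- Possible patterns: 2³ = 8.
- Positive by Table 3 with footnote 1 (any of the three): 8 − 1 = 7.
- Positive by 9.4.2 or 9.4.7 (cough or `BREATHING`): 8 − 2 = 6.
- Missed: 7 − 6 = 1, the pattern with wheeze reported, no cough and `BREATHING` not ticked.
- Of the 4 patterns that include wheeze, 3 are still counted.

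**Step 3. The same with apnoea, another footnote-1 sign, as a fourth item.**

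- Possible patterns: 2⁴ = 16. Positive by definition: 15. Positive by derivation: 12. Missed: 3 (wheeze only, apnoea only, and both, each without cough or `BREATHING`).
- Of the 8 patterns that include wheeze, 6 are counted and 2 missed.
- Reading the wheezing item as well brings the derivation to 14. Apnoea alone remains, because the SAP names no separate parent-reported item for it.

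**Step 4. If sites tick `BREATHING` whenever wheeze or apnoea is reported.** No pattern is missed. The SAP neither requires nor excludes this practice.

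**Step 5. Effect on a rate.** Pattern counts are not shares of infants. Let q be the share of true first LRTI episodes with a footnote-1 sign reported but neither `COUGH` nor `BREATHING` ticked. Then

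reported rate ≈ true rate × (1 − q).

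The SAP gives neither q nor a true rate. With an assumed true rate of 10 per 100 person-years:

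| Assumed q | Reported rate per 100 person-years |
|---|---|
| 0% | 10.0 |
| 1% | 9.9 |
| 2% | 9.8 |
| 5% | 9.5 |
| 10% | 9.0 |

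The relation is approximate: a missed infant keeps accruing person-time under 9.5.1 and may have a later episode that is counted.

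**The case against.** The strongest reply is that footnote 1 explains what the parent-reported item covers, so reading the item called difficulty breathing is the natural implementation. On that view `BREATHING` would be ticked for wheeze, and form-completion instructions that are not at hand may say so. This stands to the extent that no loss is demonstrated and zero is possible. It does not remove the gap: section 2.1 lists wheezing and difficulty breathing side by side as different symptoms, and the SAP has no sentence linking them.

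Four stronger readings are tempting, and the document does not support them:

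- *Wheezing infants are not counted.* Most wheeze patterns still qualify, through cough or `BREATHING`.
- *Wheeze by itself brings an infant to a swab.* The sampling schedule applies the trigger within an RTI, which Table 3 defines as runny nose, blocked nose or cough. The affected infant would therefore typically have nasal symptoms and no cough.
- *Every footnote-1 sign found at examination should be added.* Footnote 1 rests on parental history. Chest in-drawing in 9.4.3 is an examination finding and a severity criterion. Adding examiner-found signs would widen the entry limb beyond Table 3.
- *The comparison with the alternative definition is distorted.* Section 5.4.3.1 only repeats the incidence analyses with Table 5 and plans no formal comparison. Wheeze in Table 5 is a documented examination finding, and that table also differs in altitude cut-off (1800 m against 2500 m) and in its severity signs. Assessing how the case definitions perform is tied in section 7 to an interim analysis that only may take place.

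**Conclusion.** The mismatch between Tables 3 and 4 and sections 9.4.2 and 9.4.7 is real. Its reach is narrow: infants with reported wheeze, no cough and `BREATHING` not ticked, who also meet the SpO2 or respiratory-rate limb and, for RSV-LRTI, are RSV-positive. Each such infant is a case by definition and a non-case by derivation. For RSV-LRTI the infant is then also lost from severe and very severe LRTI when those criteria are met.

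The size cannot be derived from the SAP. The 0 to 10% range for q is an assumption chosen for illustration, so the table does not show that an under-count exists. The conclusion rests on wheezing being a separate recorded item, which section 2.1 supports, and on the absence of any rule that makes `BREATHING` cover it. The start-date inconsistency does not depend on any case being lost.

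**What to change.** 1. In 9.4.2 and 9.4.7, let the parent-reported wheezing symptom item satisfy difficulty in breathing, alongside `BREATHING`. Do not add examiner-found signs such as in-drawing.
2. Include the wheezing start date in 9.4.2.1 and 9.4.7.1, in line with the general rule in 9.4. Sections 9.4.3.1 and 9.4.4.1 follow by reference.
3. State an end-date rule for episodes that qualify through wheeze alone. Section 2.1 records no wheeze end date, so under 9.4.2.2 and 9.4.7.2 these episodes could have no end date. Their duration and the 7-day symptom-free rule in 9.4.8 would then have nothing to work from.
4. Report how many episodes qualify only through wheeze. If the number is zero, the case counts are unchanged and the report shows it.

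The cost is SAP wording, a small amount of programming on data already collected, and one added end-date convention.

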9.4.2.1. Start date of RSV-LRTI

Start dates of RSV LRTI symptoms will be pulled from the Case Assessment Visit for at least one of the following: parental report of history of cough or difficult breathing. The start date of RSV LRTI is the earliest of the start dates of the following symptoms:

- Cough

Variables will be pulled from [frmSURVEILLANCE_CONTACT] (field [ASSESS_VIS]= 'YES') and [frmSYMPTOMS_RTI] (fields [ASSESS_VIS]= 'Yes' and [sctSYMPTOMS_RTI]= 'COUGH' and [cmpCOUGH_DT]= 'SRDAT')

Or

- Difficulty Breathing

Variables will be pulled from [frmSURVEILLANCE_CONTACT] (field [ASSESS_VIS]= 'YES') and [frmSYMPTOMS_RTI] (fields [ASSESS_VIS]= 'Yes' and [sctSYMPTOMS_RTI]= 'BREATHING' and [cmpBREATHING_DT]= 'SRDAT')

9.4.2.2. End date of RSV-LRTI

End dates of RSV LRTI symptoms will be pulled from the Case Assessment Visit and will be defined as the latest date of the end dates of the following symptoms:

- Cough

Variables will be pulled from [frmSURVEILLANCE_CONTACT] (field [ASSESS_VIS]= 'YES') and [frmSYMPTOMS_RTI] (fields [ASSESS_VIS]= 'Yes' and [sctSYMPTOMS_RTI]= 'COUGH' and [cmpCOUGH_DT]= 'ENDAT')

Or

- Difficulty Breathing

Variables will be pulled from [frmSURVEILLANCE_CONTACT] (field [ASSESS_VIS]= 'YES') and [frmSYMPTOMS_RTI] (fields [ASSESS_VIS]= 'Yes' and [sctSYMPTOMS_RTI]= 'BREATHING' and [cmpBREATHING_DT]= 'ENDAT')

9.4.3. RSV severe LRTI

RSV severe LRTI cases will be reported if the person meets the case definition of RSV LRTI

AND

(The data for below can be pulled from the Case Assessment Visit OR Worsening Visits. If worsening visits took place for this episode, the most severe value of SpO₂ or RR will be used, whether it was observed in the Case Assessment Visit or the Worsening Visit.)

- SpO₂(<93% if altitude ≤2500m and <90% if altitude >2500m) (field [scOXYGEN_SATURATION_RTI] OR [scOXYGEN_SATURATION_WOR]=[SpO₂]<‘93.0% or <90%’)
OR
- Lower chest wall indrawing reported during the physical examination. (field [sctCHEST_INDRAWING_RTI]=[INDRAWING]=‘YES’) OR (field [sctCHEST_INDRAWING_WOR]=[INDRAWING]=‘YES’)

9.4.3.1. RSV Severe LRTI start date

Start dates will be defined as the earliest date of cough or difficulty breathing as described in section [9.4.2.1](#).

9.4.3.2. RSV Severe LRTI end date

End dates will be defined as the latest date of cough or difficulty breathing as described in section [9.4.2.2](#).

9.4.4. RSV very severe LRTI

RSV very severe LRTI is defined as meeting the case definition of RSV LRTI

AND

(The data for below for SpO₂ can be pulled from the Case Assessment Visit OR Worsening Visits. If worsening visits took place for this episode, the most severe value of SpO₂ or RR will be used, whether it was observed in the Case Assessment Visit or the Worsening Visit.)

- SpO₂(<90% if altitude ≤2500m and <87% if altitude >2500m) (field [scOXYGEN_SATURATION_RTI] OR [scOXYGEN_SATURATION_WOR]=[SpO₂]<‘90.0% or <87%’)
OR
- Inability to feed reported in signs and symptoms.
[sctSEVERITY_SIGNS_RTI]=[FEEDING]=‘Unable to feed’)
OR
- Failure to respond/unconscious reported in signs and symptoms.
[sctSEVERITY_SIGNS_RTI]=[CONSCIOUS]=‘The child is unresponsive to all stimuli’)

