Severe LRTI	Confirmed RSV infection	Rhonchi¹ Rales¹ Crackles Wheeze	Hypoxemia SpO₂ <93% at ≤ 1800 meters SpO₂ <90% at > 1800 meters Acute hypoxic or ventilatory failure³ Dehydration due to respiratory distress requiring IV hydration⁴ Failure to respond or unconscious

¹Term not listed in the eCRF page in this study.²Intercostal recession or chest wall indrawing are considered synonymous with and will be used as alternatives to the term "retractions," which is not listed in the eCRF page for this study.³Acute hypoxic or ventilatory failure is not listed in the eCRF page for this study. Instead, the presence of either respiratory support excluding mechanical ventilation OR requirement for mechanical ventilation or both will be used.⁴Dehydration due to respiratory distress requiring IV hydration is not listed in the eCRF page for this study. Skin turgor > 2 seconds or administration of IV fluid therapy will be used instead.

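### The severe tier is neither severe-only nor severe-or-worse: infants who are very severe only by feeding or consciousness fall outside it, and alternative severe LRTI need not be an alternative LRTI

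*SAP*

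**What the plan says.** This describes the current text, Amendment 2.

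**Main definitions (Tables 3 and 4; 9.4.2 to 9.4.4).** RSV-LRTI needs cough or difficulty breathing, then "AND at least one of following symptoms" (low SpO2 or raised respiratory rate), and confirmed RSV. Raised rate alone is enough for the second element.

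For the next tier, "RSV severe LRTI cases will be reported if the person meets the case definition of RSV LRTI" and has SpO2 <93% (<90% above 2500 m) or "Lower chest wall indrawing reported during the physical examination".

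For the top tier, "RSV very severe LRTI is defined as meeting the case definition of RSV LRTI" and one of three further items: SpO2 <90% (<87% above 2500 m), "Inability to feed reported in signs and symptoms", or "Failure to respond/unconscious reported in signs and symptoms". Table 3 has the same structure, with "inability to feed OR failure to respond / unconscious" appearing only in the very severe row.

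**Alternative definitions (Table 5).** Both rows need confirmed RSV and an auscultation finding, and each then has its own list. The LRTI list is respiratory rate, SpO2, apnea, nasal flaring, retractions and grunting. The severe list is SpO2, respiratory failure (replaced by respiratory support or ventilation), dehydration and unresponsiveness. For dehydration, "Skin turgor > 2 seconds or administration of IV fluid therapy will be used instead". The severe row does not refer back to the LRTI row.

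**Use.** Section 5.3.6.2 and Table 6 analyse the first episode of all, severe and very severe RSV-LRTI. Section 5.4.2.2 fits separate Cox models for the three. Section 5.4.3.1 repeats the incidence analyses with the alternative definitions. No section says whether a higher tier counts in a lower one.

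**The concern.** A severity tier is normally read in one of two ways. It is exclusive (severe but not very severe) or cumulative (severe or worse). The severe tier here is neither. A case that is very severe by SpO2 <90% also satisfies SpO2 <93% and is counted as severe. A case that is very severe only because the infant cannot feed or is unresponsive is not.

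The second infant is a non-event for the severe endpoint. Under 9.5.1, person-time stops at the first diagnosis of the event being analysed, so this infant also goes on accruing severe-tier person-time. The rate loses a case from the numerator and gains time in the denominator. In the severe-tier Cox model of cord-blood antibody, the infant is event-free at that episode, alongside infants who were never ill. Severe RSV-LRTI incidence is a secondary objective, and section 7 names these case definitions as possible input to those of pivotal trials, so a reader needs to know what the severe row contains.

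In Table 5 the gap lies one tier lower: the overall alternative LRTI count can leave out infants who are counted as alternative severe LRTI.

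**Working it through.** The SAP states no figure to reproduce, so the check is one of logic, followed by an illustration on assumed counts.

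**1. Main set, one infant.** RSV positive, cough, rate above the limit, SpO2 94%, no indrawing, unable to feed, altitude up to 2500 m.
- LRTI: cough, with raised rate (and 94 < 95): yes.
- Severe: 94 < 93 is false and there is no indrawing: no.
- Very severe: LRTI and unable to feed: yes.

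**2. Main set, all combinations.** Take RSV and cough as present. Let SpO2 run from 80 to 100% in 1% steps, with raised rate, indrawing, inability to feed and unresponsiveness each yes or no.

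| Altitude | SpO2 limits: LRTI / severe / very severe | Very severe | Very severe but not severe |
|---|---|---|---|
| up to 2500 m | 95 / 93 / 90 | 256 | 30 |
| above 2500 m | 92 / 90 / 87 | 226 | 39 |

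The 30 can be counted by hand. There are three ways to have inability to feed, unresponsiveness or both. At SpO2 93 or 94% the rate may be raised or not: 2 × 2 × 3 = 12. At 95 to 100% it must be raised: 6 × 1 × 3 = 18. Above 2500 m: 2 × 2 × 3 + 9 × 1 × 3 = 39. Every one has no indrawing and SpO2 at or above the severe limit. None arises from SpO2, whose limits are nested.

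**3. Table 5.** Take RSV and an auscultation finding as present, with none of the LRTI items. An infant is severe but not LRTI if SpO2 is at or above the LRTI limit and at least one of respiratory support, the dehydration proxy and unresponsiveness is present (2³ − 1 = 7 ways).
- Up to 1800 m (SpO2 95 to 100%, six values): 6 × 7 = 42 combinations.
- Above 1800 m (SpO2 92 to 100%, nine values): 9 × 7 = 63 combinations.

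Table 5 gives respiratory-rate limits only up to 6 months of age, while follow-up runs to one year. For older infants the rate route into alternative LRTI has no stated limit, which can widen this gap.

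The counts in steps 2 and 3 are logical combinations, not expected patient frequencies.

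**4. Possible size, main set.** Let S be infants severe as written, V very severe infants, and f the share of V that qualifies only by feeding or consciousness. Severe-or-worse is S + fV, and the shortfall is fV / (S + fV). The SAP gives none of these; S = 40 and the values below are assumptions.

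| V | f = 0 | f = 10% | f = 30% | f = 50% |
|---|---|---|---|---|
| 10 | 0/40 = 0% | 1/41 = 2.4% | 3/43 = 7.0% | 5/45 = 11.1% |
| 20 | 0/40 = 0% | 2/42 = 4.8% | 6/46 = 13.0% | 10/50 = 20.0% |

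No comparable illustration is offered for Table 5.

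**The case against.** The strongest reply is that nothing here is contradictory. Tables 3 and 4, 9.4.3 and 9.4.4 agree with one another, and the SAP never says that the tiers are nested. Table 6 simply lists three endpoints, and the Cox models are explicitly separate. That stands: the fault is the lack of a counting rule, not a false statement.

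A reader might infer that the plan loses its sickest infants. The documents do not support this for the main set, because each such infant is in both the all-LRTI and the very severe rows. Only the severe row is affected.

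A reader might also infer that the main and alternative sets cannot be compared tier by tier. That does not follow. Section 5.4.3.1 plans only a repeat of the incidence analyses, and the sets already differ in entry signs, altitude cut-off (2500 m against 1800 m) and number of tiers.

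The derivation rules limit the main gap. SpO2 and indrawing are taken from the case assessment or any worsening visit, while the feeding and consciousness fields named in 9.4.4 are the case-assessment ones. An infant unable to feed at assessment who later desaturates below the severe limit or develops indrawing in the same episode is therefore captured as severe.

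On Table 5, the objective is tertiary. The case of wheeze plus IV fluids alone owes something to the proxy, which drops the link to respiratory distress. That is a separate weakness, and aligning the rows would not cure it. The gap does not depend on it, since unresponsiveness is a listed severe item with no LRTI counterpart and is not a proxy.

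Finally, replacing a prespecified secondary endpoint would be out of proportion. That is accepted, and the fix leaves the endpoint in place.

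**Conclusion.** The point holds in limited form. In the main set the severe tier includes very severe cases that qualify by SpO2 or also have indrawing, and excludes those that qualify only by feeding or consciousness, so its incidence, Kaplan-Meier and Cox results have no clean interpretation. In the alternative set the affected quantity is the overall LRTI incidence, not the severe incidence.

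Both statements follow from the wording of Amendment 2 alone. Amendment 1 (its section 9.4.9) did make alternative severe LRTI conditional on alternative LRTI, but that section is not carried into Amendment 2, so Table 5 governs.

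The size is unknown. The 0 to 20% range rests wholly on assumed counts, and the true gap may be small. This is an inexpensive improvement to the reporting, not a threat to the study's conclusions.

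**What to change.** 1. Keep the severe endpoint in 9.4.3 as prespecified, and state there and under Table 6 that the tiers as written are not cumulative.
2. Add a derived flag, *severe or very severe RSV-LRTI*, true when either the 9.4.3 or the 9.4.4 criteria are met. Report its first-episode incidence, Kaplan-Meier and Cox results beside the severe row. The Cox models stay subject to the existing rule of at least 10 events per covariate.
3. Reconcile the two rows of Table 5 so that every alternative severe LRTI case is also in the alternative LRTI numerator, and write the rule into the derivations. Whether this is done by counting severe cases as LRTI or by requiring the LRTI row for severe is for the sponsor to decide.

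No clinical threshold changes and no new data are needed; the inputs come from eCRF items that the SAP already uses. The cost is a few lines of derivation text and one extra set of output rows.
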